Subjects randomized to the CD101 IV treatment group 1 will receive 1 dose of CD101 IV (400 mg) over 60 (±10) minutes on Day 1 and Day 8 and IV placebo on other study days in order to maintain the blind; subjects who require >14 days of IV therapy will receive an optional third dose of CD101 IV (400 mg) on Day 15. Subjects with IC are allowed an optional CD101 IV dose (400 mg) on Day 22 if additional therapy is required. Subjects in group 1 will receive IV placebo on other study days in order to maintain the blind. Subjects randomized to the CD101 IV treatment group 2 will receive 1 dose of CD101 IV (400 mg) over 60 (\pm 10) minutes on Day 1, 200 mg on Day 8 and IV placebo on other study days in order to maintain the blind; subjects who require >14 days of IV therapy will receive an optional third dose of CD101 IV (200 mg) on Day 15. Subjects with IC are allowed an optional CD101 IV dose (200 mg) on Day 22 if additional therapy is required. Subjects in group 2 will receive IV placebo on other study days in order to maintain the blind. Subjects may receive oral step-down therapy after ≥3 days of IV therapy, if criteria are met. Step-down therapy in both CD101 IV treatment groups will be oral placebo, in order to maintain the blind. Subjects who have already switched to oral step-down therapy will receive both oral placebo and CD101 IV on Day 8 and optional oral placebo and CD101 IV on Day 15 for subjects who require >14 days of therapy. Dosage adjustments are not allowed. Intravenous study drug is administered 24 (±2) hours after study drug was administered on the previous day.

Subjects randomized to the caspofungin group will receive IV caspofungin (70 mg loading dose on Day 1 and then 50 mg/day) for ≥ 3 days up to a maximum of 21 days for subjects with candidemia only or up to a maximum of 28 days for subjects with IC. After ≥ 3 days of IV therapy, subjects in the IV caspofungin group can be switched to oral step-down therapy if criteria are met. Step-down therapy in the caspofungin treatment group will be oral fluconazole (a loading dose of 800 mg [4 capsules] on the first day followed by 400 mg [2 capsules]/day thereafter). In order to maintain the blind, subjects who have already switched to oral step-down therapy will receive both oral fluconazole and IV placebo on Day 8, Day 15 for subjects who require ≥ 14 days of therapy. Intravenous study drug is administered 24 (± 2) hours after study drug was administered on the previous day.

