1.2.5. Study Procedures

After informed consent is obtained, all potential study participants undergo screening evaluations, which include a medical history, clinical assessments, and laboratory assessments. Mycological diagnosis of candidemia at Screening will be established by ≥1 blood culture positive for yeast or *Candida* spp., a Sponsor-approved rapid IVD test positive for *Candida* spp., or a positive Gram stain for yeast or a positive culture for *Candida* spp. from a specimen obtained from a normally sterile site from a sample taken within 96 hours before randomization. If the positive blood culture used to qualify the subject for the study is drawn >12 hours from randomization, then an additional set of blood cultures must be obtained ≤12 hours before randomization. Assessments of mycological eradication and clinical response will be performed at Day 5, Day 14 (±1 day), Day 28 (±2 days) for subjects with IC and the FU visit (Days 45-52 or Days 52-59 for IC subjects). Blood cultures should be performed daily or every other day until 2 blood cultures drawn ≥12 hours are negative without an intervening positive culture. The schedule of assessments and procedures, as outlined in the study protocol, is presented in Table 1-1.

Study participation will require from 45 to 52 days (or 52-59 days for subjects with IC) after the first administration of study drug; study drug administration from Day 1 up to Day 21 (for subjects with candidemia) or up to Day 28 (±2 days; only for subjects with IC); PK assessments on Days 1, 2, 4, 8, and 15; safety, tolerability, and efficacy assessments up to Day 21 (for subjects with candidemia only) or up to Day 28 (±2 days; only for subjects with IC); and a FU visit at Days 45 to 52 (or 52-59 days for subjects with IC).

CONFIDENTIAL Page 13 of 56

Table 1-1: Schedule of Assessments and Procedures

							Study 1	Drug A	dminis	tration,	Days						FU Visit
Study Day (window)	Screen	1 ^a	2	3	4	5	6, 7	8 ^b (±1)	9-13	14 ^b (±1)	15 ^b (±1)	16-21	22 ^{b,c} (±1)	23- 27°	28 ^{b,d} (±2)	EOT +2 days after last dose of study drug (IV and oral)	only (or Day 52-
Informed consent e	X							,		,	,		,		,	,	,
Medical history ^f	X																
Physical examination including height and weight ^g	X									X					X		X
Calculate Child-Pugh score h	X																
Modified APACHE II score with Glasgow coma score ⁱ	X																
Vital signs ^j	X	X	X	X	X	X	X ^k	X	X ^k	X	X ^k	X ^k	X	X^k	X	X	X
12-lead ECG ¹	X															X	

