3.11. Visit Windows

Study procedures should be completed within the windows provided in the Schedule of Assessments and Procedures in Table 1-1. Visit windows for each evaluation are specified in Table 3-2.

CONFIDENTIAL Page 31 of 56

Table 3-2: Visit Windows

Evaluation	Protocol-Specified Interval	Efficacy Analysis Window
Screening	Study Day -2 to Study Day 1	Study Day -2 to Study Day 1
Baseline	Study Day 1 (last measurement prior to the administration of the first dose of study drug)	Study Day 1 (last measurement prior to the administration of the first dose of study drug)
Day 5	Study Day 5 to Study Day 9	Study Day 5 to Study Day 9
Day 14 (±1 day)	Study Day 13 to Study Day 15	Study Day 13 to Study Day 21, unless study drug was terminated prior to Day 13 and had the efficacy assessment on EOT. If study drug was stopped early because the PI thought the subject was a clinical cure, the subject must be assessed during the Day 14 window.
Day 28 (±2 day)	Study Day 26 to Study Day 30 (for IC subjects)	Study Day 26 to Study Day 30 (for IC subjects)
Follow-up	Study Day 45 to Study Day 52 (Study Day 52 to Study Day 59 for IC subjects)	Study Day 38 to Study Day 59 (Study Day 45 to Study Day 66 for IC subjects)

For summaries of safety, including vital signs, 12-lead ECGs, and clinical laboratory parameters, summaries will be provided by Study Day (as appropriate) while on therapy, at the EOT and FU visits. If more than 1 measurement is available within the EOT visit window (+2 days after last dose of study drug), the measurement taken closest to last dose of study drug will be used. If more than 1 measurement is available within the FU visit (Days 45-52; Days 52-59 for IC subjects), the measurement taken on the nominal visit will be used. If no nominal FU visit is available, the earliest measurement in the window will be used.

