5.4.4. Electrocardiogram

Descriptive statistics for heart rate, PR interval, RR interval, QRS interval, QT interval, and QT interval with Fridericia correction (QTcF) at Baseline and the EOT visit and the change from baseline at the EOT visit will be summarized by treatment group for subjects in the Safety population. Change from baseline will be calculated for each subject as the value at the EOT visit minus the baseline value. QTcF will be derived programmatically using the QT and RR intervals captured in the eCRF according to the following formula (Fridericia):

$$QT_cF = \frac{QT}{\sqrt[3]{RR}}$$

The number and percentage of subjects with any post-baseline increase in QTcF and any post-baseline increase of >30 msec or >60 msec in QTcF will be summarized by treatment group. The number and percentage of subjects with a post-baseline QTcF of >450 msec or >500 msec will also be summarized by treatment group. The number and percentage of subjects with a post-baseline increase in QTcF of >30 msec resulting in a post-baseline QTcF of >450 msec or >500 msec will also be summarized by treatment group. The distribution of QTcF values (\leq 450 msec, >450 - \leq 480 msec, >480 - \leq 500 msec, and >500 msec) at EOT and the distribution of change from baseline in QTcF values at EOT (0 or less (no increase), 1-29 msec, 30-60 msec, and >60 msec) will be summarized by treatment group for subjects in the Safety population.

A by subject listing of all measurements obtained from ECG assessments will be provided.

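### The by-arm QTcF tables ignore time since active drug, which at the EOT ECG is 0-8 days for CD101 and, with few exceptions, 0-2 days for the comparator

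*SAP*

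**What the plan says.** **When the ECG is taken.** Table 1-1 (SAP 1.2.5) marks the 12-lead ECG at Screening and in the EOT column, and nowhere else. That column is headed "EOT +2 days after last dose of study drug (IV and oral". Section 1.2.3 asks for EOT assessments on the day of discontinuation when study drug is stopped prematurely. If several readings fall in the EOT window, Section 3.11 states that "the measurement taken closest to last dose of study drug will be used". The anchor is therefore study drug, not active drug.

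**When CD101 is given.** Section 1.2.1 has treatment group 1 dosed "on Day 1 and Day 8 and IV placebo on other study days in order to maintain the blind". Subjects who need longer therapy "will receive an optional third dose of CD101 IV (400 mg) on Day 15", and "Subjects with IC are allowed an optional CD101 IV dose (400 mg) on Day 22 if additional therapy is required". Treatment group 2 has the same infusion days. The Table 1-1 footnotes confirm that on the other treatment days the CD101 groups receive IV or oral placebo, while the comparator group receives caspofungin or fluconazole.

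**What is tabulated.** Section 5.4.4 summarizes ECG intervals "at Baseline and the EOT visit and the change from baseline at the EOT visit will be summarized by treatment group". It also states that "any post-baseline increase of >30 msec or >60 msec in QTcF will be summarized by treatment group", with further counts above 450 and 500 msec. None of these summaries refers to the time since CD101, caspofungin or fluconazole was last given.

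**The concern.** Safety and tolerability form the first primary objective (1.1.2), and the ECG is a named safety outcome (1.2.6.2). The EOT reading is the only scheduled post-baseline ECG, so it carries most of the QTcF evidence.

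The comparator is normally given daily, so an ECG tied to the last dose of study drug is close to active drug. CD101 is given weekly with placebo in between, so the same rule can place the ECG anywhere in the weekly interval. The by-arm rows then differ in time since active drug, and the CD101 rows also mix ECGs from the infusion day with ECGs from the end of the interval. If CD101 had an effect on QTcF concentrated soon after infusion, many CD101 readings could miss it, while an effect of the daily comparator would have a better chance of being seen. The error would run toward false reassurance.

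**Working it through.** The SAP states no figure for the interval from last active dose to ECG, so there is none to reproduce. The check is day arithmetic.

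**Inputs**
- CD101 infusion days: 1, 8, optional 15, optional 22 for invasive candidiasis (1.2.1).
- Full course: at least 14 days, up to 21 for candidemia or 28 for invasive candidiasis (1.2.1).
- EOT: k = 0 to 2 days after the last study-drug day L (Table 1-1, reading the +2 days as a window from 0 to 2).
- Early stop: EOT on the day of discontinuation, so k = 0 (1.2.3).
- Assumption: the Day 15 and Day 22 infusions are given when the course reaches those days.

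**Formulas**
- CD101: interval = (L + k) − (largest of 1, 8, 15, 22 not above L).
- Comparator: interval = k, because active drug is given daily up to L.

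**Full courses**

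| Last study-drug day L | Last CD101 day | CD101 interval (days) | Comparator interval (days) |
|---|---|---|---|
| 14 | 8 | 6-8 | 0-2 |
| 15 | 15 | 0-2 | 0-2 |
| 16 | 15 | 1-3 | 0-2 |
| 17 | 15 | 2-4 | 0-2 |
| 18 | 15 | 3-5 | 0-2 |
| 19 | 15 | 4-6 | 0-2 |
| 20 | 15 | 5-7 | 0-2 |
| 21 | 15 | 6-8 | 0-2 |
| 22 | 22 | 0-2 | 0-2 |
| 28 | 22 | 6-8 | 0-2 |

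Between Day 22 and Day 28 the CD101 interval rises by one day per day, as it does from Day 15 to Day 21. For example, L = 14 gives 14 − 8 = 6 to 16 − 8 = 8 days.

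**How many end days give 6-8 days.** Days 14 and 21 are 2 of the 8 possible candidemia end days (14 to 21). Days 14, 21 and 28 are 3 of the 15 for invasive candidiasis (14 to 28). These are counts of calendar days, not shares of subjects. The SAP gives no distribution of course lengths, so the share cannot be computed.

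**Early stops.** For L = 1 to 13 with k = 0, the CD101 interval is 0 to 6 days: 0 at L = 1 or 8, and 6 at L = 7 (7 − 1).

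**Departures from these assumptions**
- Subjects stepped down to oral therapy and discharged have a window of ±1 day on the Day 8 and Day 15 visits. For L = 14 this gives 14 − 9 = 5 to 16 − 7 = 9 days, and L = 21 gives the same 5-9.
- If the Day 15 infusion were omitted in a course of 15 to 21 days, the interval would be 15 − 8 = 7 to 23 − 8 = 15 days.
- Comparator subjects on hemodialysis receive oral fluconazole only after each dialysis session following the loading dose (1.2.1), so 0-2 days need not hold for them.

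**The case against.** Several objections have force.

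- **Overstatement.** A reader might infer that the EOT ECG always falls 6-8 days after CD101, that a peak-related effect therefore cannot appear, and that a finding of no excess would be an artefact. The documents do not support this. Courses ending on Day 15 or 22, and early stops on Day 1 or 8, can give an ECG 0-2 days after an infusion. The missing course-length distribution rules out any statement about the usual case.
- **Exposure.** The SAP gives no CD101 half-life. With assumed terminal half-lives h of 2 to 6 days, 2^(−t/h) leaves about 6% (t = 8, h = 2) to 50% (t = 6, h = 6) of the post-distribution level. That range is too wide to establish a material exposure difference. In dosing intervals, 6-8 days is about 0.9-1.1 of CD101's weekly interval, against 0-2 of the comparator's daily one, so the comparator is not reliably read at peak either.
- **Unscheduled ECGs.** Section 5.4.4 separates counts of any post-baseline change from distributions at EOT, and Section 3.11 allows ECG summaries by study day. Unscheduled readings may therefore count. Relabelling everything as EOT could discard them, so that should not be done.
- **Descriptive study.** The SAP plans no between-arm test and claims no absence of excess. This limits the severity, but the by-arm tables are still the summary ECG evidence, and the lack of a test does not make their timing comparable.
- **Schedule belongs to the protocol.** This is correct, and no new ECG is asked for. The gap is in the analysis and labelling.
- **Splitting by interval adds bias.** The interval depends on course length and early stopping, both after randomization, and Part A plans only about 30 mITT subjects per arm. The split can therefore be descriptive only. By-subject listings would let a reader derive the interval, but only by hand.

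**Conclusion.** The concern holds in a limited form and is a cheap improvement. The only scheduled post-baseline ECG is tied to the last dose of any study drug, placebo included. It falls 0-8 days after the last CD101 infusion for full courses with the optional infusions given, and 0-6 days after it for early stops. In the comparator group it falls 0-2 days after active drug, apart from the hemodialysis exception. The by-arm tables in Section 5.4.4 therefore mix unequal times since active drug and do not in general capture the period just after a CD101 infusion. A finding of no excess could reflect timing.

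This rests on reading the EOT window as 0 to 2 days and on the optional infusions being given when reached. How many subjects are affected, and how far their exposure differs, cannot be determined from the SAP. It does not show that a CD101 effect would be missed, only that the planned tables cannot tell a reader whether it could have been.

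**What to change.** In Section 5.4.4:

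1. Derive, for each post-baseline ECG, the days since the last active dose (CD101, caspofungin or fluconazole).
2. Tabulate the distribution of that interval by arm.
3. Add a descriptive summary of QTcF change and outliers by interval (0-2, 3-5, ≥6 days), labelled as a non-randomized comparison.
4. Keep the counts of any post-baseline change so that unscheduled ECGs still contribute, and state how many subjects have only the EOT reading.
5. State that the EOT table alone supports no conclusion about QTcF near CD101 peak exposure.

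The cost is one derived variable and a small extension of the tables. The dates are already collected, since Section 5.2.1 lists all IV doses and the start and stop dates of oral therapy. No new ECG is needed. The downside is small cells, intervals defined by post-randomization course length, and a more limited ECG safety statement.

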1.2.6. Definitions of Outcome Measures

1.2.6.1. Efficacy Outcome Measures

Efficacy outcome measures include overall response, mycological response and Investigator's Assessment of clinical response as well as all-cause mortality through FU, and time to negative blood culture.

Overall Response

The primary efficacy outcome measure is overall response at Day 14 (±1 day), which will be determined from the mycological response and assessment of systemic signs attributable to candidemia and/or IC (Table 1-2). Mycological response and assessment of systemic signs attributable to candidemia and/or IC are also determined at Day 5, Day 28 (±2 days; only for subjects with IC) and FU Visit (Days 45-52 or Days 52-59 for subjects with IC). The signs that may be present at baseline and attributable to candidemia and/or IC include fever, hypothermia, hypotension, tachycardia, and tachypnea. Subjects who require a change of antifungal therapy to treat candidemia and/or IC prior to a given day of the overall response assessment should have the assessment of systemic signs attributable to candidemia and/or IC moved forward to the early EOT evaluation. Assessments of systemic signs performed prior to the early EOT will be unaffected.

Table 1-2: Overall Response Categories

	Definition			
Overall Response	Mycological Response	Systemic Signs		
Success	Success (eradication/presumed eradication)*	Resolution of attributable systemic signs of candidemia and/or invasive candidiasis that were present at baseline		
	Success (eradication/presumed eradication)*	Recurrence or lack of resolution of attributable systemic signs of candidemia and/or invasive candidiasis		
Failure	Failure	Resolution of attributable systemic signs of candidemia and/or invasive candidiasis that were present at baselin		
	Failure	Recurrence or lack of resolution of attributable systemic signs of candidemia and/or invasive candidiasis		
	Failure	Assessment of systemic signs was not completed at visit or at baseline for any reason (including death)		
Indeterminate	Indeterminate	Resolution of attributable systemic signs of candidemia and/or invasive candidiasis that were present at baseline		
	Success (eradication/presumed eradication)*	Assessment of clinical signs was not completed for any reason at visit or at baseline		

^{*} Presumed eradication is defined only for a culture from a normally sterile site and is not defined for a blood culture.

The overall success rate is the proportion of subjects with success out of the total number of subjects evaluated.

CONFIDENTIAL Page 19 of 56

Mycological Response

Mycological response will be programmatically determined from the electronic case report form (eCRF) and central mycology data at Day 5, Day 14 (± 1 day), Day 28 (± 2 days; only for subjects with IC) and FU (Days 45-52 or Days 52-59 for subjects with IC), according to the definitions in Table 1-3. Determination of the identification of fungal pathogens will follow the process defined in SAP Section 4.

Table 1-3: Mycological Response Definitions

Mycological Response	Definition	
Success (eradication/presumed eradication) *	 If positive blood culture at baseline: The last blood culture drawn on or prior to the day of assessment and another blood culture drawn at least 12 hours prior are both negative for Candida spp and both blood cultures were drawn after initiation of study drug, AND 	
	 Any intervening blood cultures drawn between the 2 qualifying negative blood cultures are also negative for Candida spp. 	
	 If positive culture from a normally sterile site at baseline: Documented mycological eradication: culture on day of assessment from all normally sterile sites of baseline Candida infection (if accessible) is negative OR if no culture on the day of assessment, the most recent culture obtained after the initiation of study drug is negative, OR 	
	o Presumed mycological eradication: follow-up culture is not available (eg, normally sterile baseline site of Candida infection not accessible) or the most recent culture obtained after the initiation of study drug is positive in a subject with a successful clinical outcome (ie, did not receive rescue antifungal treatment and has resolution of systemic signs of invasive candidiasis that were present at baseline) and resolution or improvement of any baseline radiographic abnormalities due to invasive candidiasis,	
	 AND There was no change of antifungal therapy for the treatment of candidemia and/or invasive candidiasis, AND 	
	The subject is not lost to follow up on the day of assessment.	
	Note : Subjects with positive cultures from both blood and a normally sterile site will need to meet success criteria for both blood and normally sterile site to be considered success.	

CONFIDENTIAL Page 20 of 56

Mycological Response	Definition		
Failure	 If positive blood culture at baseline: The last blood culture drawn on or prior to the day of assessment or any blood culture drawn prior to and within 12 hours of the last blood culture is positive for Candida spp and both blood cultures were drawn after the initiation of study drug OR The most recent blood culture drawn at least 12 hours prior to the last blood culture is positive for Candida spp. and culture was obtained after the initiation of 		
	study drug. OR If positive culture from a normally sterile site at baseline: Documented mycological persistence: culture on day of assessment from all		
	normally sterile sites of baseline Candida infection (if accessible) is positive, OR		
	o Presumed mycological persistence: follow-up culture is not available (eg, normally sterile baseline site of Candida infection not accessible) or the most recent culture obtained after the intiation of study drug is positive in a subject without a successful clinical outcome or with continued (from baseline) radiographic abnormalities due to invasive candidiasis,		
	OR • The subject requires a change of antifungal therapy to treat candidemia, OR		
	The subject dies of any cause prior to or on the day of assessment.		
Indeterminate	• If positive blood culture at baseline: A blood specimen was not available to culture or the result was not available.		
	• If positive culture from a normally sterile site at baseline: A sterile site/fluid post-baseline specimen was not available to culture or the result was not available AND an assessment of signs of invasive candiasis was not available.		
* D 1 1' .'	Subject is lost to follow-up on the day of assessment.		

^{*} Presumed eradication is defined only for a culture from a normally sterile site and is not defined for a blood culture.

Table 1-4 provides examples of timing of the blood cultures and how these are used for determination of the mycological response.

CONFIDENTIAL Page 21 of 56

Table 1-4: Examples of Timing of Blood Cultures

	Blood Cultures	Mycological Response [1]
Example 1	Day of Assessment: Day 14 (T=0 hours) Blood cultures: T=0 (N), T= -18 (N)	Success (eradication)
Example 2	Day of Assessment: Day 14 (T=0 hours) Blood cultures: T=0 (N), T=-10 (P) T=-18 (N)	Failure
Example 3	Day of Assessment: Day 14 (T=0 hours) Blood cultures: T= -20 (N), T= -28 (N) T= -34 (P)	Failure
Example 4	Day of Assessment: Day 14 (T=0 hours) Blood cultures: T= -20 (N), T= -68 (N)	Success (eradication)

T = Time; time is relative to the date and time of assessment of mycological response.

The mycological success rate is the proportion of subjects with success (eradication/presumed eradication) out of the total number of subjects evaluated.

Clinical Response

The Investigator will make a determination of clinical response at Day 14 (±1 day), Day 28 (±2 days; only for subjects with IC), and the FU visit (Days 45-52 or Days 52-59 for subjects with IC) according to the definitions in Table 1-5. Efficacy windows are to be applied for each timepoint and are listed in Table 3-2. Subjects whose disease is progressing or who receive rescue antifungal therapy for candidemia prior to Day 14 (±1 day) will be considered a clinical failure at Day 14 (±1 day), Day 28 (±2 days; only for subjects with IC), and the FU visits. Subjects who are a clinical cure at Day 14 (±1 day) and whose symptoms recur between Day 14 (±1 day) and Day 28 (±2 days; only for subjects with IC) or FU or who receive rescue antifungal therapy will be considered a failure at the Day 28 (±2 days; only for subjects with IC) or FU visit.

CONFIDENTIAL Page 22 of 56

N = Blood culture negative for any *Candida* spp.

P = Blood culture positive for any *Candida* spp.

^[1] For Success (eradication), assumes no other criteria for failure are met.

Table 1-5: Investigator's Assessment of Clinical Response Definitions

Clinical	
Response	Definition
Cure	 Resolution of attributable systemic signs and symptoms of candidemia and/or IC that were present at baseline, AND No new systemic signs or symptoms attributable to candidemia and/or IC, AND No additional systemic antifungal therapy administered for candidemia and/or IC, AND The subject is alive.
Failure	 Progression or recurrence of attributable systemic signs or symptoms of candidemia and/or IC, OR Lack of resolution of attributable systemic signs or symptoms of candidemia and/or IC, OR Requirement for new or prolonged therapy to treat candidemia and/or IC *, OR An AE requires discontinuation of study drug therapy (IV and IV/oral) on or prior to the day of assessment, OR The subject died of any cause.
Indeterminate	Study data are not available for the evaluation of efficacy for any reason including: • Lost to follow-up, • Withdrawal of consent, • Extenuating circumstances that preclude the classification of clinical outcome of candidemia and/or IC.

AE = adverse event; IC = invasive candidiasis; IV = intravenous.

The cure rate is the proportion of subjects with a cure clinical response out of the total number of subjects evaluated.

Exploratory Mycological Response

Exploratory mycological response will be programmatically determined from the electronic case report form (eCRF) and central mycology data at Day 14 (± 1) and will be defined similarly to mycological response with only 1 blood sample used in the derivation. The responses will be derived according to the definitions in Table 1-6.

CONFIDENTIAL Page 23 of 56

^{*} Prolonged antifungal therapy is defined as therapy for the treatment of candidemia extending beyond the allowable 21 days for study drug or for the treatment of IC extending beyond the allowable 28 days of study drug. The determination of prolonged therapy will only apply to the Follow-up visit clinical response assessment.

Table 1-6: Exploratory Mycological Response Definitions

Exploratory Mycological Response	Definition	
Success (eradication/presumed eradication) *	 If positive blood culture at baseline: The last blood culture drawn on or prior to the day of assessment is negative for Candida spp and blood culture was drawn after initiation of study drug, If positive culture from a normally sterile site at baseline: Documented mycological eradication: culture on day of assessment from all normally sterile sites of baseline Candida infection (if accessible) is negative OR if no culture on the day of assessment, the most recent culture obtained after the initiation of study drug is negative, OR Presumed mycological eradication: follow-up culture is not available (eg, normally sterile baseline site of Candida infection not accessible) or the most recent culture obtained after the initiation of study drug is positive in a subject with a successful clinical outcome (ie, did not receive rescue antifungal treatment and has resolution of systemic signs of invasive candidiasis that were present at baseline) and resolution or improvement of any baseline radiographic abnormalities due to invasive candidiasis, AND There was no change of antifungal therapy for the treatment of candidemia and/or invasive candidiasis, AND The subject is not lost to follow up on the day of assessment. 	
	Note : Subjects with positive cultures from both blood and a normally sterile site will need to meet success criteria for both blood and normally sterile site to be considered success.	
Failure		

CONFIDENTIAL Page 24 of 56

Exploratory Mycological Response	Definition
Indeterminate	If positive blood culture at baseline: A blood specimen was not available to culture or the result was not available.
	 If positive culture from a normally sterile site at baseline: A sterile site/fluid post-baseline specimen was not available to culture or the result was not available AND an assessment of signs of invasive candiasis was not available. Subject is lost to follow-up on the day of assessment.

^{*} Presumed eradication is defined only for a culture from a normally sterile site and is not defined for a blood culture

Exploratory Overall Response

Exploratory overall response will be programmatically determined in same way as defined in Table 1-2 with exploratory mycological response replacing the mycological response column.

Additional efficacy outcome measures include:

- All-cause mortality (ACM) through the FU Visit: defined as death due to any cause from the date and time of randomization through the FU Visit. Subjects who did not die or are lost to follow-up will be censored in the analysis at the last date known to be alive.
- Time to negative blood culture: defined as the time, in hours from the first dose of study drug to the first of 2 negative blood cultures drawn ≥12 hours apart following the first pre-treatment blood culture confirmed positive for any *Candida* species. Determination of the identification of fungal pathogens will follow the process defined in SAP Section 4. Subjects will be censored at the earliest start date and time of receipt of an alternative antifungal (ie, other than study drug) for the treatment of candidemia received any time on/after the date and time of the first dose of study drug. If a subject is lost to follow-up prior to having 2 negative blood cultures, the subject will be censored at the date of the last blood culture.

